5.2 Data Monitoring

The trial will be conducted under the direction of the START study protocol team. Members of the protocol team are listed in [Appendix D](#). The protocol team (except those who prepare the confidential analyses) and all participating investigators will be blinded to interim results on clinical outcomes.

An independent DSMB, supported by NIAID, will meet as often as required, but at least annually, to review the general conduct of the trial and to review interim analyses of the major clinical outcomes. The monitoring plan for the review of the primary endpoint and its two major components is described below.

A sample size re-estimation will be carried out by the protocol team before the target enrollment of 4,000 participants is achieved to ensure that the planned sample size is adequate. For the sample size re-estimation, the protocol team will use only pooled endpoint data, i.e., the number and rate of AIDS* and non-AIDS events for both treatment groups combined. The protocol team will use these pooled event data and other relevant data sources to estimate the rates of AIDS*, non-AIDS, and deaths due to other causes (including unknown causes).

The DSMB will be asked to recommend early termination or modification only when there is clear and substantial evidence of a treatment difference. As a guideline, the Lan-DeMets spending function analog of the O'Brien-Fleming boundaries will be used to monitor the primary endpoint comparison.^{45,46} The DSMB will be asked not to stop the study early unless there is evidence of a significant treatment difference based on the spending function boundary for the primary endpoint and each of the two major components of the primary endpoint – AIDS*, and non-AIDS or deaths not attributed

to AIDS – are consistent (in the same direction, for example, $Z > 1.5$ for each outcome).

The DSMB will also review other relevant data that might impact the design of START, e.g., data from other completed trials, and cohorts with similarly defined target populations.

At each DSMB review, beginning with the review prior to the end of enrollment when sample size is re-estimated, futility analyses will be presented to the DSMB by the unblinded statisticians based on conditional and unconditional power. *Conditional* power incorporates the observed results by treatment group thus far (and uses the originally assumed treatment effect for future data) to calculate the conditional probability of obtaining a significant result by the end of the trial. In contrast, *unconditional* power does not take into consideration the observed treatment difference. It uses a revised estimate of the event rate in the deferred ART arm based on the observed data, the planned duration of follow-up, and the originally assumed treatment effect to calculate what the real power was at the beginning of the trial. Participants will be followed to a common closing date a minimum of 3 years after the last participant is enrolled. Thus, participant follow-up will range from 3 to 6 years, with an average follow-up of approximately 4.5 years.

Conditional and unconditional power estimates are used for two different purposes. Conditional power tells us whether we are likely to get a significant result, whereas unconditional power tells whether a null result would still be meaningful. For example, suppose the unconditional power were only 40%. Even if the true treatment benefit were as originally hypothesized, there would be a 60% chance of missing it. Therefore, a null result would not rule out the originally hypothesized treatment benefit. On the other hand, if unconditional power were high — say 90% — then a null result would effectively rule out the originally hypothesized treatment benefit.

As a guideline, we recommend that the DSMB first consider unconditional power. If unconditional power is less than 70%, the DSMB should then consider conditional power. If conditional power, given the observed data and assuming the originally hypothesized treatment effect thereafter, is less than 20%, consideration should be given to stopping the trial. We recommend early termination for futility only if both conditional and unconditional power estimates are low, i.e., only if a null result is both likely and not meaningful. It is possible that unconditional power is low in the presence of a very large treatment effect of early ART. Hence, there is a need to also consider conditional power. Such a scenario would not be grounds for stopping for futility because conditional power would probably still be high, indicating that a null result is unlikely.

In summary, the DSMB for START will be provided with the aforementioned guidelines but be expected to use their expert and independent judgment concerning early termination. It is recognized that there are a number of considerations in determining whether a trial should be stopped early. For that reason, we propose guidelines to the

DSMB, not rules. This line of thinking was summed up well by Canner in his reflections on the Coronary Drug Project: "...no single statistical decision rule or procedure can take the place of the well-reasoned consideration of all aspects of the data by a group of concerned, competent, and experienced persons with a wide range of scientific backgrounds and points of view".⁴⁷

6 Protection of Human Subjects & Other Ethical Considerations

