- uncertainty about the cost-effectiveness of early ART even if the risk-benefit ratio is favorable;
- concerns about serious complications associated with ART, e.g., cardiovascular, renal, and liver disease, that might negate the expected benefits of ART;
- side effects of ART that impact quality of life;
- concern that there could be waning adherence with long-term use of ART and consequent development of HIV resistance; and
- the potential availability of even better treatments in the future that would be easier to take and would more durably suppress the virus and carry a lower risk of the development of resistance.

[figure not shown]
Recent data from epidemiological studies indicate that the risk of AIDS is graded and persists at CD4+ levels > 500 cells/mm³. Furthermore, for a given CD4+ count, the risk of AIDS appears to be lower in patients who have started ART than in those who are ART-naïve. In addition, rates of serious non-AIDS diseases – cardiovascular, renal and hepatic disease and non-AIDS malignancies – are lower at higher CD4+ counts. Data from the SMART study, a treatment interruption trial that enrolled 5,472 participants with a CD4+ count > 350 cells/mm³, are consistent with these epidemiological data. In SMART, there was a higher rate of both AIDS and non-AIDS events in the episodic compared to the continuous ART arm. This adverse treatment effect was evident among subgroups of participants on ART at entry, participants who

previously took ART but stopped before randomization, and participants who were ART naïve. However, the latter two subgroups of participants were small.

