2.2.2 Summary of Potential Risks and Benefits

For prolonging disease-free survival, potential benefits of an early treatment strategy of initiating ART at a CD4+ cell count > 500 cells/mm³ are:

- Maintenance of a higher CD4+ cell count
- Lower risk of AIDS and non-AIDS conditions

Potential risks of the early ART strategy are:

- More side effects
- Increased risk of exhausting drug options (e.g., due to resistance)
- Increased risk of some non-AIDS events.

For prolonging disease-free survival, potential benefits of a deferred ART strategy that stipulate that ART be initiated when the CD4+ cell count declines to < 350 cells/mm³ are:

- Drugs that are safer, easier to take, and more potent and/or less susceptible to resistance development could be available when ART is eventually initiated
- Delay in any risk of adverse events of ART

Potential risks of this strategy include:

- Longer period of time at lower CD4+ cell counts and higher HIV RNA levels
- Higher risk of AIDS and serious non-AIDS conditions while ART is deferred

In addition to these potential benefits and risks of early ART for patients with a CD4+ cell count > 500 cells/mm³, there is a potential broader public health benefit of early ART. As noted in [Appendix B](#), even if transmission risk behaviors do not decrease among patients taking early ART, reduced HIV transmission would be predicted based on HIV RNA decline with ART.

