2.3.3 Composite Endpoint of AIDS* and Non-AIDS

The ultimate goal of the treatment of HIV disease is to prevent morbidity and mortality. Thus, the primary and secondary endpoints of this study are clinical outcomes rather than surrogate markers.

The primary endpoint of the START study is a composite outcome of AIDS*, non-AIDS, and death from any cause (see [Appendix E](#)). This composite outcome includes major morbid events that are life threatening and impact quality of life.

It is hypothesized that ART will positively influence both AIDS* and non-AIDS risk in the CD4+ range to be studied. Based on epidemiological studies, ART is expected to reduce the risk of AIDS* more than the risk of non-AIDS. However, the incidence of non-AIDS is expected to be greater than the incidence of AIDS*. Thus, the absolute risk reduction is expected to be similar for AIDS* and non-AIDS events.

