3.5 Sample Size and Statistical Considerations

It is estimated that 4,000 participants will be required to reliably address the primary study question. This is based on estimates of the expected event rates in the early and deferred ART groups using data from the CASCADE Collaboration and UK CHIC³⁴ with computer simulations that account for the distribution of CD4+ cell counts projected for START. These estimates and other assumptions used in calculating sample size are described in detail in [Appendix G](#) and summarized below:

- a. The primary analysis will be intention to treat using a Cox model with a single indicator for treatment group and with strata corresponding to geographic regions (North America, South America, Europe, Australasia, and Africa).
- b. Type I error is 0.05 (2-sided) and power = 0.90. Power was set at 90% for the primary endpoint, in part, to ensure that there would be adequate power to address the components of the composite endpoint, non-AIDS and fatal AIDS or non-fatal AIDS*.
- c. Participants will be enrolled over a 3-year period (2 additional years after the one year pilot phase) and followed for a minimum of 3 years resulting in an average follow-up of 4.5 years and a total study duration of 6 years.
- d. The CD4+ cell count at entry will be between 501 and 600 cells/mm³ for 70% of participants, between 601 and 700 cells/mm³ for 20%, and > 700 cells/mm³ for 10%.
- e. In the deferred ART group, the rate of the primary endpoint is 2.8 per 100 person years over the follow-up period. Non-AIDS events will be four times more common than non-AIDS deaths, and approximately 35% of reported AIDS events and 10% of

reported non-AIDS events will not meet probable or confirmed criteria (i.e., the criteria that have to be achieved to count the reported event as an endpoint). In SMART, the rates of confirmed or probable fatal AIDS or non-fatal AIDS* and of serious non-AIDS, as defined in START, were 0.4 and 2.0 per 100 person-years, respectively, in the VS group.³⁵

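### The advisory early-stopping guideline in 5.2 applies its component-consistency condition to harm as well as benefit and gives no separate guideline for harm

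*Supplement*

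**What the plan says.** Section 5.2 (Data Monitoring) sets out one efficacy guideline. For the first condition, "the Lan-DeMets spending function analog of the O'Brien-Fleming boundaries will be used to monitor the primary endpoint comparison". Section 3.5 sets the test as two-sided ("Type I error is 0.05 (2-sided) and power = 0.90"), so the boundary exists in both directions.

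The guideline then adds a second condition: "The DSMB will be asked not to stop the study early unless there is evidence of a significant treatment difference" on that boundary and unless the two major components (AIDS*; non-AIDS or death not attributed to AIDS) "are consistent (in the same direction, for example, $Z > 1.5$ for each outcome"). The value 1.5 is an example; agreement in direction is the condition itself. No sentence limits it to benefit, and no other guideline for harm is given.

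Three other parts of 5.2 matter. The DSMB may recommend modification as well as termination. A separate futility guideline looks first at unconditional power (below 70%) and then at conditional power (below 20%). All of this is described as advice to the DSMB, which is expected to use its own judgment.

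**The concern.** For a benefit claim the consistency condition is a sensible safeguard, because it prevents an early stop driven by one component. For harm it can work the wrong way.

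The protocol expects the two components to respond differently: "ART is expected to reduce the risk of AIDS* more than the risk of non-AIDS" (2.3.3). Its listed risks of early ART include "Increased risk of some non-AIDS events" (2.2.2). The Synopsis rationale cites "concerns about serious complications associated with ART, e.g., cardiovascular, renal, and liver disease, that might negate the expected benefits of ART", and 2.2.1 notes that some ART may raise cardiovascular risk. If such risks dominated, harm on the composite would come from non-AIDS events and deaths while AIDS* improved. The components would then oppose each other and the second condition would fail, however far the composite lay past the boundary. The written default would be to continue while serious disease or death was significantly more frequent, on the trial's own primary endpoint, in the early arm.

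**Working it through.** **The plan's own figure first.** Section 3.5 gives 369 events for hazard ratio (HR) 0.712, power 0.90 and two-sided 0.05. Schoenfeld: 4(1.960 + 1.282)² / (ln 0.712)² = 364.3, so 365. Freedman gives 372. The stated figure reproduces.

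**Inputs from the protocol (3.5).** Deferred-arm mix 23% AIDS* and 77% non-AIDS/death; planned AIDS* HR 0.57; target 370 events; 1:1 allocation (3.4).

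**Assumptions.** The harmful non-AIDS HRs and the look times are mine, since 5.2 states neither. O'Brien-Fleming-type bounds are |Z| = 2.963 at 50% and 2.359 at 75% information. Component statistics are treated as independent. Positive Z means early ART is worse.

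**Formulas.** With D events in total:
- AIDS* share f = 0.23(1 + HR_A) / [0.23(1 + HR_A) + 0.77(1 + HR_N)]
- component mean E(Z) = √(d/4) · ln HR, variance 1, with d = fD or (1 − f)D
- composite Z = √f · Z_A + √(1 − f) · Z_N

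**Scenario 1 in full (HR_A 0.57, HR_N 2.0, 185 events).**
- f = 0.3611 / 2.6711 = 0.135, giving 25 AIDS* and 160 non-AIDS events.
- E(Z_A) = √(25/4) · ln 0.57 = −1.406, and E(Z_N) = √(160/4) · ln 2 = 4.384.
- E(Z) for the composite = 0.368 × (−1.406) + 0.930 × 4.384 = 3.560.
- P(cross) = Φ(3.560 − 2.963) = Φ(0.597) = 0.725.
- Same direction needs Z_A > 0, so its probability is at most Φ(−1.406) = 0.080; the joint probability by simulation is 0.07.
- Z_A > 1.5 has probability Φ(−2.906) = 0.002, and the joint probability is also 0.002.

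| HR AIDS* | HR non-AIDS | Look | Crosses harm boundary | and same direction | and Z > 1.5 each |
|---|---|---|---|---|---|
| 0.57 | 2.0 | 185 events | 0.725 | 0.07 | 0.002 |
| 0.57 | 1.5 | 75% information | 0.40 | 0.02 | 0.0004 |
| 1.0 | 2.0 | 185 events | 0.83 | 0.46 | 0.065 |

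In the third row only about 31 AIDS* events are expected, so under no AIDS* effect the observed direction is close to a coin toss.

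**Where the guideline does work.** With both components harmed (HR 1.5 each, 185 events), the boundary is crossed 0.42 of the time and the components also agree in direction 0.41 of the time. The gap is specific to unlike effects on the two components.

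**Does the futility route fill the gap?** At the planned 370 events, unconditional power = Φ(√(370/4) × 0.3397 − 1.96) = Φ(1.307) = 0.904, so the first test (below 70%) is not met. Conditional power at the 50% harm boundary is about 0.0003, but it is not reached in the sequence. Unconditional power falls to 0.70 at about 214 events: Φ(√(214/4) × 0.3397 − 1.96) = Φ(0.525) = 0.70. Events would have to fall below about 58% of plan for this route to open.

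**The case against.** The strongest reply is that 5.2 binds nobody. It offers advice, keeps the DSMB's independent judgment, and says no single statistical rule can replace weighing all the data. That stands. A reader might infer that the DSMB would be obliged to continue in the face of harm; the text does not support this. What remains is that the written request runs the wrong way in a foreseeable case and would have to be overridden.

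Second, Z above 1.5 is only an example. A reader might take the 0.002 and 0.0004 in the last column as the guideline's operating figures. They are not; the same-direction column is the operative one, and in the third scenario the difference is large (0.46 against 0.065).

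Third, a reader might infer that the protocol itself names this harm scenario or calls non-AIDS toxicity its main risk. It does neither. The risks are unranked, the wording covers only some non-AIDS events, and the pattern is assembled from 2.2.1, 2.2.2, 2.3.3 and the Synopsis. Section 3.5 plans on a 24% fall in the non-AIDS/death component.

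Fourth, not every route is closed. Modification is not literally subject to the consistency condition, and futility is separate. Sections 2.3.4.1 and 3.8 already bring components, all-cause mortality and major events to interim review.

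Finally, opposing components are hard to interpret, and leaving them to judgment is defensible. For harm, however, the composite already counts any AIDS* benefit, so a crossing means net harm on the primary endpoint.

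**Conclusion.** The point holds as a gap in advisory text. Section 5.2 applies the consistency condition to stopping in either direction and gives no separate guideline for harm. When the components oppose each other, it asks the DSMB not to stop even with the composite past the harm boundary. With the planned AIDS* effect, agreement in direction alone cuts the chance of meeting the guideline from about 0.725 to 0.07, or from 0.40 to 0.02, in the two scenarios shown. These sizes rest on assumed non-AIDS hazard ratios and look times and on the 370-event target. The later section 5.3, which revises that target, is not shown, so how far the futility route was open under it cannot be judged.

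This is a worthwhile, inexpensive clarification. It is not a must-fix error, because the DSMB can act on its judgment and already receives the relevant data.

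**What to change.** In 5.2, and in the guidance given to the DSMB, state that the component-consistency condition applies to stopping for benefit of early ART. Add that crossing the composite boundary in the direction of harm is by itself enough for the DSMB to consider stopping or modification, using its judgment and the component and all-cause mortality data it already receives.

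The cost is a sentence or two. The downside is a slightly higher chance of an early stop for harm when the components disagree. The type I error for a benefit claim does not increase, and the safeguard against a premature stop for benefit is untouched.

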6.1 Local Review of Protocol and Informed Consent

Prior to the initiation of the study at each clinical research site, the protocol, all informed consent forms and the participant Information materials will be submitted to and approved by the site's IRB or IEC. Likewise, any future amendments to the study protocol will be submitted and approved by each site's IRB or IEC. After IRB/IEC approval, sites must register for START before screening potential participants, and must register for any protocol amendments. Protocol registration procedures are described in the START *Protocol Instructions Manual*.

6.2 Ethical Conduct of the Study

The study will be conducted according to the Declaration of Helsinki in its current version (2004); the requirements of Good Clinical Practice (GCP) as defined in Guidelines, EU Clinical Trials Directive (2001/20/EC), and EU GCP Directive (2005/28/EC); Human Subject Protection and Data Protection Acts; the US Office for Human Research Protections (OHRP); or with the local law and regulation, whichever affords greater protection of human subjects.

6.3 Informed Consent of Study Participants

All study participants must sign all applicable approved informed consent forms (see samples in [Appendix A](#)) prior to any study-related procedures.

6.4 Confidentiality of Study Participants

The confidentiality of all study participants will be protected in accordance with GCP Guidelines and national regulations.

7 Other Important Documents and Policies

7.1 Reference Documents

Study procedures are described in detail in the *START Protocol Instructions Manual*.

7.2 Data Collection and Monitoring

Study data will be collected on standardized case report forms. It is assumed that most data will be collected during participant visits to health-care providers. In some instances, it may be necessary to obtain and abstract hospital records. Written permission from the participant is generally required. Study data and case report forms will be made available to site monitoring personnel. Monitoring may be performed by staff from the INSIGHT International Coordinating Centers or Site Coordinating Centers or by contractors of the primary funder.

At a minimum, all items referenced in the protocol as being relevant to the research study will be recorded in the participant's research record in accordance with standard procedures. In addition, all items specifically required by the protocol will be recorded on case report forms. Items that are recommended but not required by the protocol may or may not be recorded on case report forms.

7.3 Publications and Presentations

Publications and presentations related to data obtained from this study will adhere to the INSIGHT Publications and Presentations Policy on the INSIGHT website (see [Appendix H](#)).

8 Substudies

This section describes three substudies. Not all sites will be participating in these substudies. At the sites conducting the Genomics and/or Neurology substudies, participant participation in either substudy is optional and requires a separate consent. At sites conducting the Informed Consent substudy, all participants are part of the substudy by virtue of going through the informed consent process at that site. Participants are informed that, by signing the consent form for START, they are also participating in this substudy.

8.1 Genomics Substudy

8.1.1 Background and Rationale

Despite progress in the treatment of HIV/AIDS and greater understanding of the pathophysiology of HIV infection, clinicians and researchers continue to observe unexplained differences among individuals in both the progression of untreated HIV infection and response to ART. Some of these differences can be attributed to individual participant behavior (e.g., adherence to therapy) and/or diversity of the infecting virus (e.g., viral replicative capacity), but a significant portion is likely related to individual (host) differences that are determined by individual genetics.

One example of this is the 32 base-pair deletion in the CCR5 gene that in a homozygous state confers protection against HIV infection.^{48,49,50} Another example is the association of human leukocyte antigen, HLA B*5701, with abacavir hypersensitivity reaction.⁵¹ While these findings require further understanding before routine clinical application, the first example shows how knowledge of host genetics may lead to a targeted treatment strategy based on a subject's individual risk of disease progression, and the second example shows how knowledge of genetics can lead to targeted therapy to maximize efficacy and minimize toxicity.

These examples illustrate the promise of genetic knowledge in the management of HIV/AIDS, but the next step is to refine current genetic associations while continuing to discover new associations. In order to utilize current and future advances in genetic technology to better understand the role of host genetics in the pathophysiology and treatment of HIV infection, there is a need to link genetic data with clinical outcomes data in a large, well-characterized, HIV-infected population.

